All patients admitted to the hospital in inpatient or observation status and having a CGM monitor attached will be screened and identified by providers and nurses. An order will be placed by providers to continue patient's home CGM monitor use in the hospital. A CGM patient agreement describing the hospital policy for use of CGMs will be provided to the patient for signature. (see attached agreement) Patients will be encouraged to continue to wear their CGMs in the hospital unless their presence interferes with patients' medical care. CGM presence will be recorded by nursing in patient chart under LDA (lines, drains, airway) section. A daily report will be run and these patients identified. Patients will be approached by research staff and asked to be enrolled in the study. A research consent will be reviewed with the patients and will be provided to patients for signature. Patients will be asked to continue to use their home CGMs in the hospital. If the sensor will reach the end of life patients have the option to place a new sensor and follow manufacturer recommendations for calibration and setting. Patients are responsible to provide their own sensors, transmitters, readers during the hospitalization period. If it is determined that the current sensor will interfere with the in-hospital medical and surgical care (MRI testing, procedure at the site, etc.), patient will be asked by their providers to remove the sensor and transmitter. Patients will have the option to replace the sensor after the procedure if they so desire. Patients will continue to monitor their glucose via CGM and their approved devices. For flash sensors, patients will be asked to scan their sensor at least every 8 and as needed. CGMs that require calibration will be calibrated by patients using hospital POC glucose meter readings. .

Patients alerted by their CGM about low glucose levels or fast downward or upward trending will be asked to notify their nursing staff. A POC blood glucose check will be done by nursing staff to confirm the alert or the trend. Treatment decisions will be made based on POC readings.

During hospitalization patients will continue to have their blood glucose checked with POC glucose monitor per hospital policy.

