Exclusion Criteria:

COVID-19 infection,

Infection of the skin at the CGM site requiring removal of the sensor.

Patients with altered Mental Status,

Patients unable to scan their flash CGMs at least every 8 hours.

Inability to provide written consent.

Hospitalized for less than 24h

Biospecimens

Collection of blood samples. When multiple groups are involved copy and paste the appropriate section below for example repeat section b when drawing blood from children and adults with cancer.

a. **From healthy, non-pregnant, adult subjects who weigh at least 110 pounds.** For a minimal risk application, the amount of blood drawn from these subjects may not exceed 550ml in an 8 week period and collection may not occur more frequently than 2 times per week.

Volume per blood draw: _____ ml

Frequency of blood draw (e.g. single draw, time(s) per week, per year, etc.) _____

b. **From other adults and children considering age, weight, and health of subject.** For a minimal risk application, the amount of blood drawn from these subjects may not exceed the lesser of 50 ml or 3 ml per kg in an 8 week period, and collection may not occur more frequently than 2 times per week.

Volume per blood draw: _____ ml

Frequency of blood draw (e.g. single draw, time(s) per week, per year, etc.) _____

Prospective collection of biological specimens other than blood: _____

Review of medical records, images, specimens

Check all that apply (data includes medical records, images, specimens).

Only data that exists before the IRB submission date will be collected.

Date Range for Specimens and/or Review of Medical Records:

Examples: *01/01/1999 through 12/31/2015*, or all records through *mm/dd/yyyy*.
01/01/2010 through 01/01/2022

Note: The Date Range must include the period for collection of baseline data, as well as follow-up data, if applicable.

The study involves data that exist at the time of IRB submission **and** data that will be generated after IRB submission. Include this activity in the Methods section.

Examples

- The study plans to conduct a retrospective chart review and ask subjects to complete a questionnaire.
- The study plans to include subjects previously diagnosed with a specific disease and add newly diagnosed subjects in the future.

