The study will use data that have been collected under another IRB protocol. Include in the Methods section and enter the IRB number from which the research material will be obtained. *When appropriate, note when subjects have provided consent for future use of their data and/or specimens as described in this protocol.*

Enter one IRB number per line, add more lines as needed

Data Specimens Data & Specimens _____

Data Specimens Data & Specimens _____

Data Specimens Data & Specimens _____

Data Analysis

Power analyses may not be appropriate if this is a feasibility or pilot study, but end-point analysis plans are always appropriate even if only exploratory. Provide all information requested below, or provide justification if not including all of the information.

Power Statement:

Data Analysis Plan:

Data will be described as percentages or means. Pearson χ^2 and Kruskal Wallis tests will be used to compare categorical and continuous variables respectively. Odds ratios, 95% confidence intervals and p-values will be reported for each model. All tests of significance will be 2-sided and the level of statistical significance will be set at p-value < 0.05.

Mean Absolute Relative Differences will be calculated between matched pairs of POC monitors and the closest CGM reading (within 5 minutes of POC). Additionally, level of agreement between the two devices will be examined with Bland-Altman plots, with particular attention focused on detection agreement in range (70-180 g/dl). Poisson or negative binomial regression will be utilized to assess count variables such as number of alarms, nurse notification, and hypo or hyperglycemia events adjusting for patient characteristics. Finally, longitudinal analysis will be conducted to determine differences associated with medications, clinical parameters or diagnosis. Analysis will seek to define if there are any differences between CGM and POC measurement based on these changes.

Endpoints

Primary: CGM accuracy - mean absolute relative difference (MARD)

Secondary:

- CGM accuracy at detection of hypo or hyperglycemia episodes when compared with POC monitors. (MARD for readings <70g/dl, >180g/dl, >250g/dl)
- CGM accuracy for detecting time in range (70-180 g/dl MARD).
- Number of CGM alarms and the clinical result of these alarms: nurse notification, treatment of hypo or hyperglycemia episodes, treatment for rapid declining glucose alarms.

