- Time in therapeutic range for glucose as measured by CGM and POC glucose monitor.
- Detection of medications, clinical parameters or diagnoses that would interfere with CGM reading.
- Effect of CGM use on length of hospital stay, post-surgical duration of hospitalization

Clinical safety measures:

- Number of sensors with failure.
- Number of sensors removed for procedure.
- Number of sensor related skin reaction (contact dermatitis, infection)

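### The count models for alarms, nurse notifications and glucose events state no exposure term although stay and sensor wear vary, and the promised odds ratios do not fit these models

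*Combined protocol and SAP*

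**What the plan says.** The Data Analysis Plan uses Poisson or negative binomial regression for "count variables such as number of alarms, nurse notification, and hypo or hyperglycemia events adjusting for patient characteristics". It does not list the characteristics. Earlier in that section it states: "Odds ratios, 95% confidence intervals and p-values will be reported for each model". Tests are two-sided at 0.05. Target accrual is 150 and the Power Statement is blank.

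Other sections show that observed time differs between patients:

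- **Stay.** The only limit is an exclusion: "Hospitalized for less than 24h". No maximum or fixed observation window is given. The secondary endpoints include "Effect of CGM use on length of hospital stay, post-surgical duration of hospitalization".
- **Start of wear.** The subject population includes patients whose monitor can be placed after admission.
- **End of wear.** Methods says "If the sensor will reach the end of life patients have the option to place a new sensor", and "Patients are responsible to provide their own sensors, transmitters, readers during the hospitalization period". Where the sensor would interfere with care, the "patient will be asked by their providers to remove the sensor and transmitter", and replacing it afterwards is optional.
- **Failure.** The clinical safety measures count failed sensors and sensors removed for procedures.

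Testing intensity also varies. After a patient reports an alert, "A POC blood glucose check will be done by nursing staff to confirm the alert or the trend".

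**The concern.** A count depends on both the rate and the time over which events could be seen. If that time varies and the model ignores it, a characteristic that only lengthens stay can be reported as raising alarms, notifications or events. One that only goes with sensor removal can be reported as lowering alarms. Such links are plausible here, because medical and surgical patients are enrolled together and procedures are a stated reason for removal.

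The effect measure is a second problem. Exponentiated coefficients from Poisson and negative binomial models are ratios of rates or mean counts. These are the only regression models the plan names; no logistic model appears. A rate ratio labelled as an odds ratio would be misread.

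**Working it through.** The plan gives no figure to reproduce. Its inputs are N = 150, two-sided alpha 0.05 and a minimum stay of 24 h. Rate, dispersion, stay distribution and wear gaps below are all assumed.

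**1. Direction of the error.** Let both groups have the same rate λ per day, with observed time T independent of a patient's own rate. Then the mean count in a group is λ × mean(T). Without an offset, the fitted ratio tends to mean(T in group 1) / mean(T in group 0). For mean stays of 4 v 4.4, 5 and 6 days this is 4.4/4 = 1.10, 5/4 = 1.25 and 6/4 = 1.50. If mean(T) is equal in the groups, the ratio is 1.

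**2. Size by simulation.** There were 1,000 studies per scenario, with two groups of 75. Stay was 1 day plus a gamma variable (shape 1.5) scaled to the stated mean. Counts were gamma-Poisson with equal true rates, fitted by maximum-likelihood negative binomial with a Wald test. Cells show the geometric-mean ratio and the share with p<0.05; the Monte Carlo standard error is at most 1.6 percentage points.

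| Mean stay (days) | 2/day, dispersion 0.5: no offset | with offset | 0.3/day, dispersion 1.0: no offset | with offset |
|---|---|---|---|---|
| 4 v 4 | 1.00, 9% | 1.00, 6% | 1.01, 6% | 1.00, 6% |
| 4 v 4.4 | 1.11, 13% | 1.00, 5% | 1.10, 8% | 1.00, 4% |
| 4 v 5 | 1.26, 32% | 1.00, 6% | 1.27, 18% | 1.02, 6% |
| 4 v 6 | 1.51, 71% | 1.01, 5% | 1.49, 39% | 0.99, 5% |

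With an 80:20 split at 2/day and no offset, 4 v 4.4, 5 and 6 days give 1.09 (11%), 1.22 (19%) and 1.47 (50%). A different set of assumptions (1/day, dispersion 0.5, stay of 1 day plus an exponential) gives 1.26 (26%) at 4 v 5 days and 1.64 (75%) at 3 v 5 days.

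**3. Wear time.** With equal 4-day stays at 2/day, 10% less wear in one group gives a false ratio of 0.90 (13%), and 25% less gives 0.75 (44%). An offset of wear time restores 1.00 (5–6%). An offset of stay would leave the 0.75 in place, so the choice of denominator matters.

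**4. Choice of model.** With the offset, 4 v 4 days and 2/day, plain Poisson rejects in 43% of studies, against 6.6% with robust errors.

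**5. When the offset itself misleads.** The with-offset columns assume a constant rate, so their good performance is built in. Suppose instead that the rate falls as exp(−t/τ), identically in both groups. The mean count is then proportional to 1 − exp(−1/τ)(1 + θ/τ)^(−1.5), where θ = (mean stay − 1)/1.5. For τ = 4 days and stays of 4 v 6 (θ = 2 and 3.33), this is 1 − 0.424 = 0.576 and 1 − 0.314 = 0.686. The ratio without an offset is 0.686/0.576 = 1.19. Simulation at 4 v 6 days gave:

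| τ (days) | no offset | with offset |
|---|---|---|
| 2 | 1.08, 8% | 0.77, 33% |
| 4 | 1.18, 19% | 0.83, 26% |
| 8 | 1.27, 39% | 0.90, 13% |

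The offset does better when decline is slow and worse when it is fast.

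**6. Odds ratio against rate ratio.** For a Poisson count with reference mean μ and a true rate ratio of 1.5, the odds ratio for any event is (e^(1.5μ) − 1)/(e^μ − 1). At μ = 0.2, 1 and 3 this is 1.58, 2.03 and 4.66. The two measures are not interchangeable.

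**The case against.** **The plan is silent on exposure, which does not rule it out.** The models get one sentence in a minimal-risk template, and an analyst might add an offset unprompted. This stands as far as it goes: the defect is that no exposure term is stated. But undefined patient characteristics cannot fairly be read as including exposure. The variables listed in Methods are demographics, comorbidities, labs and vitals, and medications, and stay is treated as an outcome. Choosing between stay and wear after seeing the data would also change the answer.

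**An offset is not a guaranteed cure.** This stands. Methods has treatment guided by the admitting team during the stay, so rates may fall over time. The Background associates poor glucose control with longer stay, so stay may depend on the outcome. A reader might infer that an offset secures a 5% error rate; step 5 shows otherwise. This is a reason to add a sensitivity analysis, and it does not justify ignoring observed time.

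**A total per stay is a legitimate summary.** It is, for describing alarm burden. It does not support a claim that a characteristic changes how often alarms occur.

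**The odds-ratio sentence is generic.** It precedes the count models, and the later longitudinal analysis has no stated model type. Correcting it changes no fit. It does, however, cover every model as written.

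**The size is wholly assumed.** True. The largest rejection rates need a 50% difference in mean stay. At a 10% difference, rejection in equal groups is 8–13%, against 6–9% with no difference.

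**Conclusion.** The point holds for the secondary count analyses. As written, characteristics associated with stay or wear get false ratios of about the ratio of mean observed times, assuming a constant rate and observed time independent of the patient's own rate. Characteristics unrelated to observed time are not biased. The size in this trial cannot be known from the documents. The odds-ratio wording is a definite but smaller mismatch.

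Two stronger readings are not supported. A reader might infer that Aim 2 is undermined by the missing offset, or would be answered once it is added. Aim 2 asks whether alerts would prevent episodes; these models relate counts to patient characteristics, with no comparator described, so an offset does not make them a test of prevention. A reader might also infer that the primary result is affected. The primary endpoint is the MARD from matched readings, which does not use these models.

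**What to change.** Amend the Data Analysis Plan before analysis:

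- **Model.** Use negative binomial, or Poisson with robust errors.
- **Alarms and notifications.** Offset by log(CGM wear hours during the enrolled stay). Report how many patients have zero wear hours, since they cannot enter this model.
- **Glucose events.** State which method detects the event. If CGM, offset by log(hours with CGM data), counting only hours with data for flash sensors. If POC, offset by log(monitored patient-time). POC testing is intermittent, so add a sensitivity analysis using the number of POC tests, and separate events found on alert-triggered checks.
- **Constant-rate assumption.** Add a sensitivity analysis by day of stay, or over a fixed early window such as the first 24–48 h.
- **Reporting.** Give rate ratios with 95% intervals for these models in place of odds ratios, and list raw totals per stay descriptively.

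No new data source is needed: Methods already plans access to or download of CGM data, and stay is in the health record. The cost is the work of defining and deriving observation time for each count, including gaps from late placement, removal, failure and missed scans. A rate ratio does not describe total burden per stay, which is why the raw totals stay in the report.

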hypoglycemia may lead to neurological damage, cognitive decline, seizures and coma. Additionally, the management of the diabetic complications doubles the inpatient cost per capita compared to non-diabetic patients.

Current standard of care in the hospital recommended by the national guidelines is the bedside point-of-care (POC) glucose capillary testing performed before meals and at bedtime. This approach however does not provide continuous 24-h glucose measurement and fails to detect nocturnal or asymptomatic hypoglycemia or hyperglycemia, all of which are common insulin therapy complications.

Continuous Glucose Monitoring (CGM) represents an alternative with the potential to assist making personalized therapy decisions. It measures levels of interstitial glucose every 5-15 min, which provides better assessment of nocturnal or asymptomatic hypoglycemia or hyperglycemia and shows glycemic patterns following treatment interventions. The ability to monitor glucose more frequently will also allow for timely interventions, and thus hyperglycemia and hypoglycemia episodes can be reduced. There have been studies demonstrating improved glycemic control in insulin-treated DM patients using CGM in outpatient setting, and even a few studies describing the use of CGM in non-ICU hospitalized patients.

Prospective studies evaluating the use of the newer CGMs in non-critically ill hospitalized patients are lacking. The aim of our study therefore was to compare the accuracy of patient's own CGM monitor worn in the hospital in detecting blood glucose levels by comparing them with those measured by a POC blood glucose capillary test.

Study Design and Methods

Methods: *Describe in lay terms, completely detailing the research activities that will be conducted by Mayo Clinic staff under this protocol.*

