Treatment of the DM and associated complications, dosing of the insulin, change from PO to insulin treatment and back to PO medications during hospitalization or at discharge will be guided by the admitting team with as needed help from the inpatient Endocrinology Consultation Service.

Decisions about insulin dosing or other medication use designed to treat hyper or hypoglycemia episodes or underlying diabetes mellitus will be made based on hospital POC blood glucose meters and not based on CGM readings alone.

Patients will be asked to give the research team “provider access” to their cloud CGM software, or to allow the team to download their CGM data prior to discharge if their reading devices do not automatically synchronize with the cloud software.

CGM data will be compared with POC blood glucose monitoring obtained in the hospital. Different patient variables (demographics, comorbidities, labs and vitals, administered medications) will be collected from electronic health record and will be evaluated to determine if they would interfere with CGM readings. The accuracy of CGM for glucose measurement in the hospital will be calculated.

Outcomes measured:

CGM accuracy when compared with POC monitors.

CGM accuracy at detection of hypo or hyperglycemia episodes when compared with POC monitors.

Number of CGM alarms and the clinical result of these alarms: nurse notification, treatment of hypo or hyperglycemia episodes, treatment for rapid declining glucose alarms.

Materials:

CGMs (sensors, transmitters and readers) belong to patients

Provider access to cloud CGM program will be granted to the research team by the patient.

Personnel:

A research assistant that will identify the patients and enroll them into the study.

Subject Information

Target accrual is the proposed total number of subjects to be included in this study at Mayo Clinic. A “Subject” may include medical records, images, or specimens generated at Mayo Clinic and/or received from external sources.

Target accrual: 150

Subject population (children, adults, groups): Admitted adult medical and surgical patients with Diabetes Mellitus type I or II that have their own CGM monitor present on admission or able to be placed after admission.

Inclusion Criteria:

Patients with Type 1 or 2 Diabetes Mellitus,

Patients 18 years of age or older,

Patients admitted under medical or surgical services.

Patients treated with diet alone, insulin (SQ, insulin pump) or oral hypoglycemic medications.

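### The search for factors that interfere with CGM specifies no adjustment for glucose level or rate of change, so drugs that shift glucose can be flagged as sensor interferents or can mask real ones

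*Combined protocol and SAP*

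**What the plan says.** The Endpoints section lists as secondary: "Detection of medications, clinical parameters or diagnoses that would interfere with CGM reading". The analysis is given at the end of the Data Analysis Plan: "longitudinal analysis will be conducted to determine differences associated with medications, clinical parameters or diagnosis", followed by "Analysis will seek to define if there are any differences between CGM and POC measurement based on these changes". The difference may be signed, absolute or relative, and no model or covariates are named.

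Five other statements bear on the point:

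- Candidate factors (Study Design and Methods): "Different patient variables (demographics, comorbidities, labs and vitals, administered medications) will be collected from electronic health record". They are to be examined as possible causes of interference, not as adjustment terms.
- The only adjustment in the plan belongs to the count regressions: "hypo or hyperglycemia events adjusting for patient characteristics".
- Glucose bands appear in the accuracy endpoints ("MARD for readings <70g/dl, >180g/dl, >250g/dl", and a separate in-range MARD) but are not carried into the interference analysis. I read the printed g/dl as mg/dl.
- The accuracy metric is relative: "Mean Absolute Relative Differences will be calculated between matched pairs of POC monitors and the closest CGM reading (within 5 minutes of POC").
- The Background says of CGM: "It measures levels of interstitial glucose every 5-15 min". The comparator is capillary glucose. Study Design and Methods adds a POC check when the CGM warns of low or fast-moving glucose.

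**The concern.** Two things other than interference can change the disagreement between CGM and POC.

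- **Glucose level.** Relative error has glucose in its denominator. Unless sensor error grows in strict proportion to glucose, the absolute relative difference falls as glucose rises.
- **Rate of change.** If interstitial glucose trails capillary glucose, a gap opens whenever glucose is moving.

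Many drugs under study act on exactly these two quantities: eligible patients include those on insulin or oral hypoglycemic medication, and administered medications are candidate interferents. Alert-triggered POC checks also enrich the matched pairs for low and fast-changing glucose, where both effects are largest.

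The endpoint asks what disturbs the sensor. An analysis without these terms can instead pick out what changes glucose. A glucose-raising drug can appear to improve accuracy and a glucose-lowering one to worsen it. A real interferent that also raises glucose can go unseen.

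**Working it through.** The plan has no figure to reproduce: the Power Statement is blank, and no error SD, lag or effect size is given. From the documents I take N = 150 and two-sided alpha 0.05. All other inputs are assumptions.

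**1. Level effect.** For zero-mean normal error of constant SD, MARD = SD x sqrt(2/pi) / glucose, with sqrt(2/pi) = 0.798.

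| SD (mg/dl) | MARD at 120 | MARD at 220 |
|---|---|---|
| 10 | 6.6% | 3.6% |
| 15 | 10.0% | 5.4% |
| 20 | 13.3% | 7.3% |

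A drug that moves glucose from 120 to 220 appears nearly to halve the error. If the SD is a fixed fraction of glucose, the ratio is constant and this effect vanishes.

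**2. Lag effect.** Gap = rate x delay. At 2 mg/dl/min and 5-10 minutes the gap is 10-20 mg/dl, which is 6.7-13.3% of 150 mg/dl. With 12% random error, MARD is 0.12 x 0.798 = 9.6% at no gap and rises to 11.0% and 14.9%. This is an upper bound for a drug effect, because it puts every pair at that rate.

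**3. False flags with no true interference.** Assumptions: 16 pairs per patient, 25% of patients on the drug, mean glucose 165 mg/dl, within-patient SD 45, meter CV 5%, and least squares with patient-clustered standard errors. Sensor error SD is either 15 mg/dl + 4% of glucose (mixed) or 12% of glucose (proportional). There were 400 runs per row, so the Monte Carlo standard error at 5% is sqrt(0.05 x 0.95 / 400) = 1.1 points. The outcome is absolute relative difference; the adjusted model adds a POC spline, rate and absolute rate.

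| Drug effect on glucose | Error | Lag | Unadjusted | Adjusted |
|---|---|---|---|---|
| None | mixed | 10 min | 7.2% | 6.0% |
| +25 mg/dl | mixed | 0 | 56.0% | 5.0% |
| +50 mg/dl | mixed | 0 | 96.5% | 6.0% |
| -30 mg/dl | mixed | 0 | 76.5% | 6.2% |
| 1.5x rate SD | proportional | 10 min | 50.0% | 5.0% |
| +50 and 1.5x rate SD | mixed | 10 min | 83.5% | 6.0% |
| Mean rate +0.5 mg/dl/min | proportional | 10 min | 6.0% | 6.5% |
| +50 mg/dl | proportional | 0 | 6.5% | 6.8% |

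In the three mixed-error rows without lag, the average spurious effect was -1.2, -2.1 and +2.1 percentage points for +25, +50 and -30 mg/dl. The mean-rate shift does not show in the absolute outcome but does in the signed difference (mg/dl): 68.5% flagged unadjusted, 7.2% after level and rate adjustment.

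A further simulation gave the same picture: about 49-100% unadjusted against 5-12% adjusted for absolute relative difference where error was not purely proportional or lag was present, and 99% falling to 8% for the signed difference under a 10-minute lag with a mean rate shift.

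**4. Adjusting the signed difference for level is unsafe.** The CGM-POC difference and average share the same errors. With independent errors, their error covariance is (sensor variance - meter variance) / 2. At 165 mg/dl under the mixed assumption, the sensor SD is 15 + 0.04 x 165 = 21.6 and the meter SD is 0.05 x 165 = 8.25, giving (466.6 - 68.1) / 2 = 199 (mg/dl)^2, not zero. A drug that shifts glucose then acquires a false coefficient.

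With no lag, between-patient SD 25, a cubic in the average plus rate and absolute rate, and 300 runs, false flags for the signed relative difference were:

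| Error | Drug effect | Unadjusted | Adjusted for average and rate |
|---|---|---|---|
| mixed | +50 | 8% | 44% |
| mixed | +25 | 6% | 19% |
| mixed | -30 | 6% | 27% |
| proportional | +50 | 5% | 86% |

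The inflation is smaller, but still present, when part of the sensor error is common to a patient's readings. Adjusting the signed difference (mg/dl) for POC in the step 3 simulation gave 7-14% in the level-shift rows, against 5-8% unadjusted. The absolute relative difference stayed at 5-7% whether level was POC or the average.

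**The case against.** The strongest reply is that the plan does not exclude adjustment. It names no model, and neither its clinical parameters nor its labs and vitals rule out glucose as a term. A reader might infer that the sponsor has chosen an unadjusted analysis and that glucose-altering drugs will be flagged. The documents support neither step. They are silent on the model, and the outcome depends on error structure, lag and outcome scale, none of which they state. This part of the objection stands: the accurate words are not specified and can be flagged.

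It is also true that a glucose denominator alone creates no disagreement: without measurement error or lag the difference is zero at every level. The level effect needs error that is not proportional to glucose and an absolute outcome. Routine POC checks before meals and at bedtime need not fall at fast-changing glucose, so a steady 2 mg/dl/min in all pairs overstates the lag effect.

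What does not stand is that silence is harmless. It leaves the choice of terms until after the data are seen, and nothing in the plan supports the one error structure under which the choice would not matter.

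**Conclusion.** The point holds as an omission with a cheap remedy. As written, the interference analysis cannot separate a factor that disturbs the sensor from one that changes glucose. With no true interference, and with mixed error or a lag that the drug's effect engages, unadjusted absolute relative difference gave about 50-97% false flags in the main simulation, against 5-7% after adjustment for level and rate. With purely proportional error and no lag, the unadjusted rate was already 6-7%. Apart from N = 150 and alpha 0.05, every input is an assumption, so these figures show what can happen, not what this trial will find.

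A reader might also infer that the main accuracy result is compromised. It is not: the primary endpoint is overall MARD, which does not use this analysis. The consequence is confined to one secondary endpoint, where the trial could name common glucose-acting drugs as interferents or miss a real one.

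**What to change.** Replace the general statement with a prespecified mixed or patient-clustered longitudinal model of the matched pairs:

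1. **Lead outcome: absolute relative difference.** Adjust for glucose level (a flexible term or the plan's own bands) and for the signed and absolute CGM rate of change over the 15-30 minutes before the POC value.
2. **Second outcome: signed relative difference.** Adjust for rate of change only. Do not condition it on the CGM-POC average or on POC alone; if level adjustment is wanted, use a measurement-error method.
3. **Reporting.** Give unadjusted and adjusted results side by side and repeat the analysis in slow-change pairs, for example within +/-1 mg/dl/min. Describe a factor as a possible interferent only if its association persists.

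The cost is analysis-plan wording and variables derived from the CGM data already to be downloaded. Pairs without a recent CGM reading will lack a rate value; report their number. With readings every 15 minutes, a 15-30 minute window spans only one or two intervals, so rate is measured with error and some residual bias will remain.
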